### 4.6 TERMINATION OF THE CLINICAL STUDY

If the investigator, the sponsor, the Medical Monitor, or the IDSMC becomes aware of conditions or events that suggest a possible hazard to subjects if the clinical study continues, then the clinical study may be terminated. The clinical study may be terminated at the sponsor's discretion at any time also in the absence of such a finding.

Conditions that may warrant termination of the clinical study include, but are not limited to:

- The discovery of an unexpected, relevant, or unacceptable risk to the subjects enrolled in the clinical study.
- Failure to enroll subjects at the required rate.
- A decision of the sponsor to suspend or discontinue development of ZX008.

## 4.7 REPLACEMENT OF SUBJECTS

Enough subjects will be enrolled in the trial to ensure that approximately 105 subjects are randomized into the T+M Period. Randomized subjects will not be replaced.

### 4.8 ELIGIBILITY FOR EXTENSION STUDY

Subjects who complete the 12-week Maintenance Period of this study will be eligible to enroll in a planned, separate, open-label extension trial of ZX008 if they meet Inclusion/Exclusion criteria for that study regarding their suitability for continued participation in a trial of Confidential

Page 42 of 175

fenfluramine.

Subjects must complete the entire 12-week Maintenance Period in order to be offered enrollment into the separate, open-label extension trial of ZX008. Those subjects who do not complete the 12-week Maintenance Period of the study may, on a case-by-case basis, be eligible for entrance into the separate open-label extension study after consideration of the circumstances of the early termination and the potential benefit-risk of continued participation in a ZX008 trial. The decision whether to permit open-label extension study participation resides solely with the sponsor, who may consult with the site investigator, the IPCAB and/or the IDSMC.

### 5. INVESTIGATIONAL MEDICINAL PRODUCT INFORMATION

ZX008/matching placebo will be administered in the current study. A brief description of the ZX008 product is provided below (Table 2).

Table 2: Investigational Medicinal Product – ZX008

	Study Product
Substance Code	ZX008
Active Substance (INN)	Fenfluramine Hydrochloride
Trade Name	Not applicable
Formulation (including dosage form and strength)	Solution 1.25, 2.5, and 5 mg/mL
Route/Mode of Administration	Oral
Manufacturer	PCI Pharma Services on behalf of Zogenix
	International Limited

### 5.1 IDENTITY OF INVESTIGATIONAL MEDICINAL PRODUCT

ZX008 drug product is an oral aqueous solution of fenfluramine hydrochloride buffered to pH 5 and provided in concentrations of 1.25 mg/mL, 2.5 mg/mL, and 5 mg/mL. The excipients selected have been approved for use in the formulations of currently marketed drug products and are considered to be safe. The solution formulations will be suitably flavored and colored, and will contain preservatives and a thickening agent. The product is sugar free and is intended to be compatible with a KD.

The formulation will be provided in bottles with tamper-evident, child-resistant caps. The clinical trials material will be supplied in 1 bottle size with nominal fill volume of 120 mL. Matching placebo also will be provided. Doses to be studied include 0.2 mg/kg/day and

0.8 mg/kg/day divided into two daily (BID) doses, up to a maximum of 30 mg/day. An intermediate dose of 0.4 mg/kg/day will be used for titration. The concentration of ZX008 oral solution received by subjects (1.25 mg/mL, 2.5 mg/mL, and/or 5 mg/mL) will be randomized across the 3 available concentrations in order to ensure blinding.

Confidential Page 43 of 175

If the parent/caregiver is unable to administer the full dose due to spillage (eg, dose was spilled during measuring, subject spit dose out during administration), he/she should attempt to give the full dose noting the extra amount used to fulfill the dose. **Care must be taken not to overdose.** If the amount spilled is not known, the parent/caregiver should not give additional medication to avoid potential overdose.

### 5.1.1 Labeling and Packaging

The ZX008 product will be packaged and labeled according to current International Conference on Harmonization (ICH), Good Manufacturing Practices (GMP), and Good Clinical Practices (GCP) guidelines, and national legal requirements.

Dosing directions for the product can be found in the IMP handling instructions for the study subjects and for the investigator.

# 5.2 DESCRIPTION OF REFERENCE TREATMENT, COMPARATOR, AND/OR PLACEBO

Placebo solution is identical in aspect and composition to ZX008 and is composed of identical ingredients used in the ZX008 formulation, except that it does not contain the active ingredient, fenfluramine hydrochloride.

No comparators or reference treatments will be used.

### 5.2.1 Labeling and Packaging

Placebo solution will be packaged in an identical manner to ZX008. The matching placebo product will be packaged and labeled according to current ICH, GMP, and GCP guidelines, and national legal requirements.

Dosing directions for the product can be found in the IMP handling instructions for the study subjects and for the investigator.

# 5.3 SHIPMENT AND STORAGE

IMP will be supplied to the study sites by the sponsor or its delegate.

All IMP will be transported, received, stored, and handled strictly in accordance with the container or product label, the instructions supplied to the research site and its designated pharmacy, the site's standard operating procedures, and applicable regulations. IMP must be stored separately from normal hospital or practice inventories, in a locked facility with access limited to the investigator and authorized personnel. The investigator must ensure that the IMP is dispensed only to subjects enrolled in this study according to this study protocol.

Appropriate storage temperature and transportation conditions will be maintained for the study drug from the point of manufacture up to delivery of the study drug. Study medication must be stored at 15-25°C (59-77°F) with excursions of 5-30°C (41-86°F) permitted; do not freeze.

Storage and handling instructions of the IMP maintained at the subject's home are described in

Confidential Page 44 of 175

the subject's IMP handling instructions.

All unused IMP will be saved by the site for final disposition according to the sponsor's directive.

### 5.4 IMP ACCOUNTABILITY

The investigator or delegate will confirm receipt of all shipments of the IMP in writing using the receipt form(s) provided by the sponsor or vendor.

Assignment of ZX008 or placebo to the subject will be handled through an interactive voice randomization (IVR) or Interactive Web Response (IWR) platform. The investigator or delegate will be required to register the subject through IVR/IWR and all study medication will be assigned to the subject through the IVR/IWR. The IVR/IWR will also maintain a log of all received and dispensed medication.

All supplies must be accounted for throughout the study using the drug accountability form provided by the sponsor before the start of the study. At the end of the study, the dated and signed (by the investigator or delegate, eg, pharmacist) original drug accountability form must be retained at the study site as verification of final drug accountability.

Records for the delivery of the IMP to the study site, the inventory at the study site, the use by each subject (use by subject will be documented in the subject diary), and the destruction or return of the IMP to the sponsor must be maintained by the investigator (or delegate). The records will include dates, quantities, batch numbers, and unique code numbers assigned to the IMP and to the subjects. The investigator must maintain records documenting that subjects were provided with the doses of the IMP specified in this study protocol. Furthermore, the investigator must reconcile all IMPs received from the sponsor. The investigator must provide reasons for any discrepancies in drug accountability. Forms will be provided by the sponsor to ensure standardized and complete drug accountability.

### 5.5 TREATMENT ADMINISTRATION

### 5.5.1 Randomization

Upon completion of the Baseline Period, subjects who qualify for the study will be randomized (1:1:1) in a double-blind manner to receive 1 of 2 doses of ZX008 (0.2 mg/kg/day, 0.8 mg/kg/day; 30mg/day maximum) or placebo. The randomization will be stratified by age (<6 years, ≥6 years) to ensure balance across treatment arms, and at least 40% of subjects will be in each age group. Subjects will be assigned a randomization number by the IVR/IWR system upon confirmation that subject qualifies for enrollment in the Titration Period. Once a randomization number is assigned to a subject, the site will record the subject's initials and identification number on the corresponding study drug bottles. Each bottle will contain the assigned treatment (ZX008 0.2 mg/kg/day, ZX008 0.8 mg/kg/day, or placebo). ZX008 and placebo will be identical, thus rendering the study drug and placebo indistinguishable. For each IMP bottle and randomization number assigned, the following information will be recorded on the drug

Confidential Page 45 of 175

accountability form: subject initials, unique bottle number, date each bottle is assigned, and drug used and unused during the study.

### 5.5.2 Titration Period

The investigator (or delegate) will dispense IMP only to subjects included in this study following the procedures set out in this study protocol.

Study medication will be administered as equal doses BID in the morning and in the evening approximately 12 hours apart, with food. Each dose should be separated by a minimum of 8 hours and a maximum of 12 hours. A missed dose of study medication may be taken later up to 8 hours before the next scheduled dose; otherwise, the missed dose should not be given.

Administration of the IMP will be based on the randomized dose and subject's weight (kg) at Visit 3 (Study Day -1). At Visit 8 (Study Day 43), if the subject's weight (kg) has changed ±25% of the weight at Study Day-1, the IMP dose will be recalculated. Subjects should be dosed using the oral dosing syringe provided.

In order to maintain the blind across all dose groups (Section 5.6) and allow step titration to the high dose, the dose for each subject will be titrated starting with a dose of ZX008 0.2 mg/kg/day (or placebo equivalent) BID. After 4 days at this dose level (Study Day 5), subjects randomized to the ZX008 0.8 mg/kg/day group will increase their dose to 0.4 mg/kg/day (maximum 30 mg/day) while doses in the other two groups will remain constant. On Study Day 9, the dose for the 0.8 mg/kg/day group will increase to the target dose or a maximum of 30 mg/day. The titration is expected to take a total of 14 days (Table 3). A new bottle of IMP will be started by the subject at each level of the titration step. See Section 5.6 for more information about the volume of ZX008 or placebo to be administered.

**Table 3** Titration Algorithm

,00	Titration Step 1	Titration Step 2	Titration Step 3		
Randomized Group	ndomized Group Study Day 1-4		Study Days 9-14		
ZX008 0.2 mg/kg/day	ZX008 0.2 mg/kg/day	ZX008 0.2 mg/kg/day	ZX008 0.2 mg/kg/day		
ZX008 0.8 mg/kg/day	ZX008 0.2 mg/kg/day	ZX008 0.4 mg/kg/day	ZX008 0.8 mg/kg/day		
Placebo Placebo Placebo Placebo					
Note: maximum daily dose of ZX008 is 30 mg					

### 5.5.3 Maintenance Period

After completion of the Titration Period, subjects will enter the Maintenance Period and continue to receive the randomized dose of ZX008 or placebo and be treated for an additional 12 weeks. Study medication will continue to be administered BID in the morning and in the evening, approximately 12 hours apart, with food. Each dose should be separated by a minimum of 8 hours and a maximum of 12 hours. A missed dose of study medication may be taken later up to 8 hours before the next scheduled dose; otherwise, the missed dose should not be given.

Confidential Page 46 of 175

### 5.5.4 Taper Period

Subjects who complete the Maintenance Period and will not be continuing into the open-label extension study, and subjects who discontinue from the study early, will be tapered off of study medication. Study medication will be administered as equal doses BID in the morning and in the evening approximately 12 hours apart, with food. Each dose should be separated by a minimum of 8 hours and a maximum of 12 hours. A missed dose of study medication may be taken later up to 8 hours before the next scheduled dose; otherwise, the missed dose should not be given. IMP should be administered using the oral dosing syringe provided.

In order to maintain the blind across all dose groups, all subjects who do not continue into the open-extension study will participate in a dose-tapering procedure over the course of 8 days. On the first day of the tapering period subjects in the ZX008 0.8 mg/kg/day group will decrease to a dose of ZX008 0.4 mg/kg/day BID (maximum 30 mg/day). After 4 days at this dose level (Study Day 5), subjects randomized to the ZX008 0.8 mg/kg/day group will decrease their dose to 0.2 mg/kg/day. Subjects in the ZX008 0.2 mg/kg/day group will decrease their dose to placebo on the first day of tapering while doses in the placebo group will remain constant throughout the tapering procedure. On Study Day 9, all subjects will stop taking study medication. The taper is expected to take a total of 8 days (Table 4). A new bottle of IMP will be started by the subject at each level of the taper step.

Table 4: Taper Algorithm

Randomized Group	Taper Step 1 Day 1-4 after study completion or early termination	Taper Step 2 Days 5-8 after study completion or early termination		
ZX008 0.2 mg/kg/day	Placebo	Placebo		
ZX008 0.8 mg/kg/day	ZX008 0.4 mg/kg/day	ZX008 0.2 mg/kg/day		
Placebo Placebo Placebo				
Note: maximum daily dose of ZX008 is 30 mg.				

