#### **Duration of Treatment:**

All subjects will receive ZX008 or matching placebo for up to approximately 16 weeks (Titration Period=2 weeks; Maintenance Period=12 weeks; Taper/Transition Period=2 weeks). After completion of the Maintenance Period, eligible subjects may enroll in the open-label extension study, after completion of the transition. Subjects who do not enroll in the open-label extension study will undergo a taper off of study medication (doses will be administered in a blinded fashion similar to the titration, i.e., doses will be decreased in 4-day increments). Follow-up cardiovascular safety assessments, including ECG and ECHO, will be performed 3 to 6 months following the last dose of study medication.

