The Baseline Period is comprised of the initial screening for the study and the assessment of baseline seizure activity recorded daily in the diary. The procedures to be completed at the Screening visit may be completed in a single day b: Subjects who are discontinued early and those who complete the study and choose not to enroll in the separate open-label extension will be tapered off study medication over an up to 2-week period.

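### The taper is set by randomised arm alone, so a 0.8 mg/kg/day subject who stops during early titration has the dose doubled, or not lowered, at the first taper step

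*Protocol*

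**What the plan says.** Section 5.5.4 applies the taper to completers who do not enter the extension, and it says that "subjects who discontinue from the study early, will be tapered off of study medication". It adds that "all subjects who do not continue into the open-extension study will participate in a dose-tapering procedure over the course of 8 days". For the high-dose arm, on the first taper day "subjects in the ZX008 0.8 mg/kg/day group will decrease to a dose of ZX008 0.4 mg/kg/day BID", and from the fifth day the dose falls to 0.2 mg/kg/day.

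Table 4 sets this out with one row per randomised group. Its first dose column is headed "Taper Step 1 Day 1-4 after study completion or early termination", so early stops are expressly included. Footnote b to Table 1 repeats that early discontinuers "will be tapered off study medication over an up to 2-week period". The synopsis describes the taper as one in which "doses will be decreased in 4-day increments".

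Section 5.5.2 and Table 3 give the upward path. Every active subject starts at 0.2 mg/kg/day. On Day 5, "subjects randomized to the ZX008 0.8 mg/kg/day group will increase their dose to 0.4 mg/kg/day". Then "On Study Day 9, the dose for the 0.8 mg/kg/day group will increase to the target dose", subject to the 30 mg/day cap.

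Nothing in the protocol modifies the taper for a subject who has not yet reached target.

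**The concern.** Table 4 was evidently written for a subject leaving from 0.8 mg/kg/day, yet it is applied by arm whatever dose the subject is taking. For the high-dose arm the two algorithms collide during the first 8 days. The first taper dose is then higher than, or equal to, the dose being stopped, which contradicts Section 5.5.4's own description of that step as a decrease.

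What is at stake is safety. An adverse event is one of the listed reasons for withdrawal in Section 4.5. A child withdrawn for one in the first days and put on the standard taper could have the daily dose raised after the decision to stop.

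The blind makes this hard to catch. Under Section 5.6, site staff, the Medical Monitor and the sponsor know neither the allocation nor the concentration. Under Section 5.4, the IVR/IWR assigns every bottle. A site that chooses a taper has nothing in front of it showing that the taper bottle holds a higher dose for that subject.

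**Working it through.** **Inputs**

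- Titration, 0.8 arm (Section 5.5.2, Table 3): 0.2 mg/kg/day on Days 1-4, 0.4 on Days 5-8, 0.8 from Day 9.
- Taper, 0.8 arm (Section 5.5.4, Table 4): 0.4 mg/kg/day for 4 days, then 0.2 for 4 days.
- Cap: 30 mg/day.
- Body weight for the worked example: 20 kg, an assumption for illustration only.

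**Formula.** Daily dose = min(rate × weight, 30 mg). Step ratio = first taper dose ÷ dose at the time of stopping.

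**The protocol's own path first.** From target at 20 kg: 0.8 × 20 = 16 mg/day, then 0.4 × 20 = 8, then 0.2 × 20 = 4. The first ratio is 8/16 = 0.50. The stated decrease is reproduced.

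**The same rule from each titration step**

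| Dose when stopped | First taper step | Ratio | At 20 kg (mg/day) |
|---|---|---|---|
| Step 1: 0.2 mg/kg/day | 0.4 | 2.00 | 4 → 8 → 4 |
| Step 2: 0.4 mg/kg/day | 0.4 | 1.00 | 8 → 8 → 4 |
| Step 3 or target: 0.8 mg/kg/day | 0.4 | 0.50 | 16 → 8 → 4 |

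**Effect of the cap.** The doubling is exact while 0.4 mg/kg/day is within 30 mg, that is up to 30/0.4 = 75 kg. At 80 kg it is 16 → 30 mg/day, a ratio of 30/16 = 1.88. The raised dose is half the arm's target up to 30/0.8 = 37.5 kg. Above that weight the target itself is capped, so 0.4 mg/kg/day is more than half of it (at 50 kg, 20 of 30 mg/day).

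**Active drug given after the stop**

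- Table 4 as written: 4 × 0.4 + 4 × 0.2 = 2.4 mg/kg, from either step.
- Taper from the dose being taken: stopped on Step 1, placebo throughout = 0; stopped on Step 2, 4 × 0.2 = 0.8 mg/kg.
- Difference: 2.4 − 0 = 2.4 mg/kg for Step 1, and 2.4 − 0.8 = 1.6 mg/kg for Step 2.
- At 20 kg: 48 mg against 0, and 48 mg against 16 mg.

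**Window.** The first scheduled clinic visit after randomisation is Day 15 ± 4 (Table 6), so Day 11 at the earliest; Days 4 and 8 are phone contacts. Under Section 6.2.9, taper drug is dispensed at the early-termination clinic visit. The problem therefore needs an unscheduled early-termination visit before the Day 9 increase. Section 4.5 makes such a visit possible, because it asks for end-of-study procedures at, or as near as possible to, the time of discontinuation.

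**The case against.** The strongest reply is that Section 4.5 leaves the choice between an immediate stop and a taper to the site investigator, after discussion with the Medical Monitor. For a Step 1 stop, an immediate halt gives the same active drug as the proposed fix, namely none. A site also knows the study day and has Tables 3 and 4, so it could work out that nobody is above 0.4 mg/kg/day before Day 9 and avoid the taper for any withdrawal in that window. This is a real safeguard, but a partial one. It offers stop or taper, not a corrected taper. Taper is the written default, and each blinded site would have to notice the conflict for itself.

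It is also fair that the path is uncommon and the exposure modest. No scheduled clinic visit falls in the window. If 0 to 5% of the 35 subjects in the arm stopped on Days 1-8 (an assumption; the protocol gives no figure), that is at most 0.05 × 35 = 1.75, about 2 subjects, before removing immediate stops. The worst case is 4 days at 0.4 mg/kg/day, below the 0.65 to 3.6 mg/kg/day that Section 1.5 cites from earlier paediatric use. The Step 2 case holds the dose rather than raising it, and is the lesser part of the point. All of this stands, and it limits the severity.

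Two supporting texts carry little weight. The synopsis line can be read as summarising a taper from target. The pregnancy rule in Section 4.4.2 hardly applies, since no scheduled test falls within Days 1-8. The point needs neither: Section 5.5.4 and Table 4 conflict with Table 3 on their own.

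Finally, the IVR/IWR specification and handling instructions are not shown and might deal with this. A system built to Table 4 would reproduce the error, and one that departs from it would contradict the protocol. The text needs correcting either way.

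**Conclusion.** The concern holds. As written, the rule doubles the daily dose for 4 days in a 0.8-arm subject tapered from titration Step 1 (a little less than doubling above 75 kg). It gives no first decrease in one tapered from Step 2. The avoidable active drug is 2.4 and 1.6 mg/kg respectively.

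This rests on the protocol's wording, on a taper being chosen over an immediate stop, and on that taper starting before the Day 9 increase. How many subjects would be affected cannot be derived from the protocol, and the number is probably small. The comparison over the combined Titration and Maintenance Periods is untouched. It should be corrected because it is a dosing instruction that can do the opposite of its purpose in a withdrawn child, and the correction is cheap.

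**What to change.** State in Section 5.5.4, Table 4 and the IVR/IWR rule that the taper starts one step below the dose being taken when the subject stops. For the 0.8 arm:

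- **Stopped on Step 1 (0.2 mg/kg/day):** placebo for both taper steps, as Table 4 already does for the 0.2 arm on the same dose.
- **Stopped on Step 2 (0.4 mg/kg/day):** 0.2 mg/kg/day for 4 days, then placebo for 4 days.
- **Stopped from Day 9 onward:** the present row.

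All arms keep two bottles over 8 days, so the blind is preserved.

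The cost is one sentence, two table rows and an IVR/IWR rule that uses the arm and the titration step at the time of stopping. Only dose levels already in Tables 3 and 4 are used. No new strength, visit or unblinding is needed.

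While editing, the sponsor may also note that at 75 kg or more a subject on the capped target goes from 30 to 30 mg/day at the first taper step, because 0.4 × 75 = 30.

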### 5.5.5 Transition Period

Subjects who complete the Maintenance Period and will be continuing into the open-label extension study will be transitioned from double-blind study medication to open-label ZX008 (Table 5). Study medication will be administered as equal doses BID in the morning and in the evening approximately 12 hours apart, with food. Each dose should be separated by a minimum of 8 hours and a maximum of 12 hours. A missed dose of study medication may be taken later up to 8 hours before the next scheduled dose; otherwise, the missed dose should not be given. Study medication should be administered using the oral dosing syringe provided.

All subjects entering the open-label extension study will be transitioned from their blinded daily dose (placebo, 0.2 mg/kg/day, 0.8 mg/kg/day, or 30 mg/day) to the 0.2 mg/kg dose during the 2-week interval between Visits 12 and 13, without breaking the blind. The IVR/IWR system will assign two bottles of IMP to the subject, one for each step in the transition. A new bottle of IMP will be started by the subject at each level of the transition step. See Section 5.6 for more

Confidential Page 47 of 175

information about the volume of ZX008 or placebo to be administered.

**Table 5:** Transition Algorithm

Dose Group in Double-Blind	Transition Step 1 Day 1-4 after Visit 12	Transition Step 2 Days 5-14 after Visit 12
ZX008 0.2 mg/kg/day	ZX008 0.2 mg/kg/day	ZX008 0.2 mg/kg/day
ZX008 0.8 mg/kg/day	ZX008 0.4 mg/kg/day	ZX008 0.2 mg/kg/day
Placebo	ZX008 0.2 mg/kg/day	ZX008 0.2 mg/kg/day
Note: maximum daily	dose of ZX008 is 30 mg.	

Subjects who had been randomized to placebo increase their dose to 0.2 mg/kg/day beginning on day 1 of the transition (the day following Visit 12; Study Day 100.) Subjects who had been randomized to 0.2 mg/kg/day will continue to receive that dose. Subjects who had been randomized to 0.8 mg/kg/day or were receiving the maximum dose of 30 mg/day decrease to a dose of ZX008 0.4 mg/kg/day. After 4 days at this dose level (day 5; Study Day 104), these subjects will decrease their dose to 0.2 mg/kg/day. Subjects will report to the clinic on day 15 (Study Day 113) for enrollment into the open-label extension study.

